## 5.6 RECRUITMENT PLAN FOR PROSPECTIVE STUDIES

**Table 5** – Recruitment plan including estimated number of eligible patients, total number of participants expected to be approached or screened via the study kiosk and online data capture tool.

Recruitment Plan	
Estimated number of potentially eligible study participants, from prior research and examining medical records: ~400 eligible patients at OSU, UIC and Duke, Hopkins ~200 eligible at Pitt	1600 at clinical sites
Our community-based organizations reach 10000+ patients. Conservative estimate is that 50% of those are eligible adults with chronic pain	5000 through CBO networks
Total number of study participants expected to be approached in clinic (n = 450) or complete online screener (n = 100)	550
Of those screened, total number of study participants expected to be eligible	450
Of those eligible, total number participants enrolled via clinics (n = 300) and CBOs online (n = 50)	350
Target sample size	350
Total number of clinical sites that will enroll participants	5
Projected rate of enrollment	Month 7 start of enrollment
Estimated percentage of participant dropout	10-15% complete no follow-up assessments 30-40% stop using intervention before reaching Module 4

**Table 6.** Estimated final racial/ethnic and gender enrollment table (N = 350)

Race	Male (N)	Female (N)	Total (N)
American Indian/ Alaska Native			
Asian			
Black/African American	170	170	340
Hawaiian/Pacific Islander			
White			
Multirace	5	5	10
Ethnicity	Male (N)	Female (N)	Total (N)
Hispanic (Latino/Latina)			
Non-Hispanic	175	175	350

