### 9.4.2 ANALYSIS OF THE PRIMARY ENDPOINT(S)

We will employ linear mixed models for the primary outcome of pain intensity and the secondary outcome of pain interference (Hypothesis 1) as a function of time, study arm (cCBT vs. m-Education), time-by-study arm interaction, study site, and baseline depression level (PHQ-9  $\leq$  10 vs. PHQ-9  $>$  10). We will account for multiple observations for each participant by including a random effect for subject. Additionally, baseline variables with large clinically meaningful between-arm differences will be included as covariates. Contrasts will be estimated to assess the impact of cCBT and m-Education intervention on 6month improvements in pain. As a secondary investigation, we will use the same linear mixed models to address whether the 6-month improvements are sustainable to 12 months.

We will answer Hypothesis 2 using a similar analytic strategy. Depression (PHQ-9) will be modeled as a function of time, study arm, time-by-study arm interaction, and study site. We will account for multiple observations for participant by including a random effect for each subject.

Healthcare utilization (Hypothesis 3) will be compared between study arms using generalized linear models to account for count data (i.e., Poisson regression) for each of the following: the number of opioid prescriptions, number of ED visits, and number of hospitalizations over 12 months post study entry. Predictors will include study arm, study site, and baseline depression level. The corresponding health care utilization in 12 months prior to study entry will be entered as a covariate in each model. We will offset each model by participant's time on the study.

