#### 9.4.6 SUB-GROUP ANALYSES

The objective of Aim 2, examining heterogeneity of treatment effect (HTE), is to determine whether the intervention works better for some than for others. We again pre-specify our analysis plan and will examine differences in main outcomes for patients with high ( $\text{PHQ-9} > 10$ ) versus low ( $\text{PHQ-9} \leq 10$ ) depression. These subgroups are most relevant so that end results can meaningfully inform patients about what works best for whom, and in turn, better support individuals as they seek treatment for pain. Furthermore, in examining differential impact of the interventions, based on these subgroups, providers, payers, and other decision makers can target resources in a manner that best meets the needs of those in need of services, reduces variations in practice, and improves health outcomes. We will augment the primary analysis models for pain intensity with relevant main effects for baseline depression level, and 2- and 3-way interactions with study arm and time. Of primary interest will be the significance of the 3-way interaction (time-by-study arm-by-baseline depression level). If significant, we will present treatment effect estimates and measures of variability in the form of confidence intervals within each subgroup. Two-sided tests of level 0.05 of the interactions between intervention and HTE subgroup will allow us to test whether depression moderates impact of intervention on pain outcomes. Although

hypotheses are stated with direction, we will conduct two-sided tests to be conservative. For all of the above described models, we will focus on the 6-month outcome.

---

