Sample Size Calculation. For the primary test of comparative effectiveness of digital CBT versus mobile education (m-Education) for the trial, the power calculation is based on the comparison of intervention groups for the main outcome of the 6-month change in pain interference. Specifically, our sample size of 350 participants enables 80% power to detect a difference of 0.37 SDs between study arms on 6-month changes. This detectable effect is also applicable to key secondary outcomes, such as pain intensity and depression, as measured by the PHQ-9. Our calculations account for 15% attrition at 6 months.

Hypotheses. Our study hypotheses are:

H1: cCBT will confer greater benefit on pain outcomes at 6 months, compared to m-Education. The primary outcome of the proposed trial is change in pain interference at 6 months. The main secondary outcome will be change in average weekly pain intensity. We will also explore sustainability of the intervention effects at 12 months.

H2: cCBT will confer greater benefit on depressive symptoms at 6 months, compared to m-Education.

H3: cCBT will confer greater decreases in health care utilization (opioid prescriptions, acute care visits) and opioid misuse behaviors (Current Opioid Misuse Measure – COMM) over 12 months, compared to m-Education.

Analysis Sets. All analyses will be under the framework of intention-to-treat, such that all randomized participants are included regardless of initiation or adherence to interventions. However, we will conduct sensitivity analyses restricting to participants who were randomized with confirmation of sickle cell disease.

Study Outcomes.

Primary Pain Outcome: Pain Interference

Patient Reported Outcomes Measurement Information System Pain Interference assesses the effect of patient-reported pain on relevant aspects of a person's life and may include the extent to which pain hinders engagement with social, cognitive, emotional, physical, and recreational activities. This measure will only be completed at baseline and 3, 6, and 12 months.

Secondary Pain Outcome: Daily Pain Intensity

Participants will be asked to enter their daily pain via a mobile website. They will receive reminder notifications via text messages for 2-week periods at baseline and 3, 6, and 12 months. However, between these automated-reminder periods, participants will be encouraged to continue entering their pain scores on the mobile pain web app.

Other Secondary Outcomes

Painimation

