Painimation is an electronic pain assessment tool that allows users to better communicate pain symptoms. Patients are provided with a selection of animations (painlessions) that they use to describe the quality of their pain. The painimation can be adjusted to reflect pain intensity. Screenshots of the Painimation app illustrate the splash screen, paintable body image, and selection of painimations to indicate the quality and intensity of pain.

Medical Outcomes

For patients recruited at one of the six clinical sites, we will evaluate objectively measured opioid medication prescriptions and refills and emergency department visits or hospitalizations for pain episodes. We will work in collaboration with PCORnet to collect data retrospectively (12 months before enrollment) and prospectively (12 months after enrollment) from patients' electronic health records. These data will allow us to track opioid medication use, health care use, and laboratory values (e.g., hemoglobin level), as well as other key clinical outcomes. For patients recruited from our CBO partners or on the web, we will only evaluate their medical records to confirm their SCD diagnosis if they do not receive their SCD care at one of the participating clinical sites.

Current Opioid Misuse Measure

Current Opioid Misuse Measure is a self-report measure to monitor indicators of current aberrant drug-related behaviors in patients with chronic pain on opioid therapy. This measure will be completed only at baseline and 12 months.

Patient Health Questionnaire

PHQ-9 assesses the degree of depression severity. The PHQ-9 total score is for nine items, all rated as 0 (not at all) to 3 (nearly every day), with total scores ranging from 0 to 27. Scores of 5, 10, 15, and 20 represent cut-off points for mild, moderate, moderately severe, and severe depression, respectively. This measure will only be completed at baseline and 3, 6, and 12 months.

Generalized Anxiety Disorder Scale-7

GAD-7 evaluates the severity of anxiety. The GAD-7 total score for the 7 items ranges from 0 to 21. Scores of 5, 10, and 15 represent the cut-off points for mild, moderate, and severe anxiety, respectively. This measure will only be completed at baseline and 3, 6, and 12 months.

Adult Sickle Cell Quality of Life Measurement Information System Emotional Functioning and Social Impact Scales

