Linear mixed models will be employed for the primary outcome of pain interference as a function of time, study arm (digital CBT vs Education), time \times study arm interaction, study site, and baseline depression level (PHQ-9 \leq 10 vs PHQ-9 $>$ 10). We will account for multiple observations for each participant by including a random effect for the subject. In addition, baseline variables with large, clinically meaningful between-arm differences will be included as covariates in the secondary analyses. Contrasts will be estimated to assess the impact of digital CBT and education intervention on 6-month improvements in pain interference. As a secondary investigation, we will use the same linear mixed models to address whether the 6-month improvements are sustainable for 12 months. The analytic strategy for the key secondary outcome of pain intensity will be identical to that of the primary outcome. As the confirmation of a sickle cell diagnosis may not be made immediately after randomization, we will conduct an a priori sensitivity analysis restricting eligible participants with the confirmation of SCD.

Analysis of Secondary Outcomes

Secondary outcomes such as PHQ-9, Current Opioid Misuse Measure, GAD-7, Adult Sickle Cell Quality of Life Measurement Information System, and SCSES will be analyzed using similar linear mixed models with time, study arm, time×study arm interaction, study site, and baseline depression level as fixed covariates and a random effect for each subject. Health care use will be compared between study arms using generalized linear models to account for count data (i.e., Poisson regression) for each of the following: the number of opioid prescriptions, number of emergency department visits, and number of hospitalizations over 12 months after study entry. Predictors will include the study arm, study site, and baseline depression level. The corresponding health care use in the 12 months before study entry will be entered as a covariate in each model. We will offset each model by the participant's time in the study.

Subgroup Analysis

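### The three health-care-use counts are tested by Poisson regression with no provision for overdispersion, so their standard errors are too small if patients' rates vary beyond the covariates

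*SAP*

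**What the plan says.** Hypothesis H3 in the SAP states that "cCBT will confer greater decreases in health care utilization (opioid prescriptions, acute care visits") over 12 months than the education arm. The outcomes modelled are "the number of opioid prescriptions, number of emergency department visits, and number of hospitalizations over 12 months after study entry", and the method is "generalized linear models to account for count data (i.e., Poisson regression) for each of the following". Protocol section 9.4.2 matches it: "Healthcare utilization (Hypothesis 3) will be compared between study arms using generalized linear models to account for count data (i.e., Poisson regression"). The predictors are arm, site and baseline depression level (PHQ-9 split at 10), with an offset for time in the study. On earlier use the SAP adds: "The corresponding health care use in the 12 months before study entry will be entered as a covariate in each model".

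Neither document mentions overdispersion, a scale parameter, a negative binomial or quasi-Poisson model, robust standard errors, a dispersion check or a fallback model. The subject random effect belongs to the linear mixed models. The normality check and transformations in protocol section 9.4.1 concern continuous variables. The SAP also places the opioid misuse score (COMM) under H3, but that score gets a linear mixed model, so this point does not reach it.

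**The concern.** A Poisson model sets the variance of each count equal to its mean. If patients with the same covariate values still have different underlying rates, the variance exceeds the mean. The model-based standard error of the arm effect is then too small, and a chance difference in use is more likely to be reported as an effect.

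The population makes such variation plausible, though the documents do not demonstrate it. Protocol section 5.1 admits any sickle cell genotype and ages 18 to 65. Patients can qualify through frequent pain, through prescribed long-acting or daily opioids, or both. Neither genotype nor opioid status at entry is a planned predictor.

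At stake are the H3 claims about opioid prescribing and acute care. If the variance method is not fixed in advance, it would have to be chosen after the results are visible.

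**Working it through.** The plan gives no event rate, dispersion, alpha level or power for these counts, so there is no planned figure to reproduce.

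**Inputs from the documents**
- Patients with utilization data: clinical-site patients only (SAP, Medical Outcomes: "For patients recruited at one of the six clinical sites, we will evaluate objectively measured opioid medication prescriptions and refills").
- Number: 300 (protocol section 5.6, Table 5: "total number participants enrolled via clinics (n = 300) and CBOs online (n = 50")). This is the protocol's five-site plan; the six sites come from the SAP.
- Allocation 1:1; covariates as listed in the plan.

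**Assumptions**
- Two-sided 5% level. Protocol section 9.4.6 states "Two-sided tests of level 0.05 of the interactions between intervention and HTE subgroup", but no level is given for H3.
- Stable patient rates following a gamma distribution, with assumed shape *a* and mean *m* events a year. Equal 12-month exposure.

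**Step 1: what the prior-year count leaves behind.** Given a prior-year count *x*, the patient's rate is gamma with shape *a* + *x* and rate parameter *a*/*m* + 1. The next year's count then has variance equal to its mean times

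φ = 1 + 1/(*a*/*m* + 1) = 1 + *m*/(*a* + *m*),

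which always exceeds 1. For *a* = 2:
- *m* = 1: 1 + 1/3 = 1.333
- *m* = 2: 1 + 2/4 = 1.500
- *m* = 4: 1 + 4/6 = 1.667

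**Step 2: actual size of a nominal 5% Poisson test.** Size = 2 × (1 − Φ(1.96/√φ)), which gives 9.0%, 11.0% and 12.9%. Because φ stays below 2 under these assumptions, the size stays below 16.6% when the covariate fits well.

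**Step 3: simulation of the planned model.** True null, 300 patients, six sites, shape 2, 20,000 replicates. The plan does not say how the prior-year count enters, so both forms were run.

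| Prior count | Mean | Dispersion | Poisson rejects | Sandwich rejects | SE ratio, sandwich/Poisson |
|---|---|---|---|---|---|
| log(count + 1) | 1 | 1.32 | 8.8% | 5.6% | 1.13 |
| log(count + 1) | 2 | 1.50 | 11.5% | 6.0% | 1.20 |
| log(count + 1) | 4 | 1.68 | 12.9% | 5.6% | 1.27 |
| raw | 1 | 1.32 | 9.1% | 5.7% | 1.14 |
| raw | 2 | 1.50 | 12.2% | 6.0% | 1.22 |
| raw | 4 | 1.74 | 15.5% | 6.1% | 1.33 |

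The log rows agree with Step 2. The raw row at mean 4 exceeds it (15.5% against 12.9%) because a raw count under a log link also fits the mean poorly. That excess is covariate misfit, not patient variation.

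**Step 4: sensitivity** (means 1, 2, 4; 3,000 replicates for shapes 4 and 1)
- Shape 4, log form: Poisson 7.1%, 8.4%, 11.0%; sandwich 4.8% to 5.9%.
- Shape 1, log form: Poisson 11.0%, 12.6%, 15.4%; sandwich 6.1% to 6.7%.
- Shape 1, raw form (includes misfit): Poisson 12.6%, 18.2%, 25.3%; sandwich 6.4% to 7.5%.
- No patient variation, mean 2: Poisson 4.8% to 4.9%; sandwich 5.2% to 5.3%.
- Under-dispersed binomial counts, mean 12: at dispersion 0.5, Poisson 0.7% and sandwich 5.6% to 5.7%; at 0.8, Poisson 2.8% to 3.0% and sandwich 5.5%.

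**Step 5: variation that the prior year does not inform.** Here the residual variance was set directly to μ(1 + *k*μ), with five sites and 1,000 runs per setting. Poisson rejected 4.1% at *k* = 0 (μ = 2), 19.6% at μ = 2, *k* = 0.5, and 43.3% at μ = 4, *k* = 1. Pearson-scaled errors gave 4.5%, 6.3% and 8.6%; sandwich errors gave 4.8%, 6.0% and 7.1%. This confirms the direction. Its size is not comparable with Step 3, because *k* is residual variation by construction.

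**The case against.** The strongest objection is that nothing in the documents shows the condition to be met. Every percentage rests on an assumed shape, mean and alpha. The error vanishes without residual variation and reverses for regular counts, which repeat prescriptions may well be. This stands: the point is a conditional risk, and its size cannot be fixed from the documents.

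The plan also removes part of the variation already, through the prior-year count, site, depression level and the offset. That is correct and is built into the figures. The offset handles only exposure, however, and the prior-year count leaves a dispersion of about 1.3 to 1.7 in the shape 2 setting.

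A further argument is that the SAP names the model but not the variance estimator, so robust errors would not contradict it. True, but Poisson regression with nothing added would ordinarily be run with model-based errors, and both documents introduce it with i.e., not as an example.

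Finally, these are secondary outcomes, and quasi-Poisson or negative binomial models would also serve. Both remarks are fair. They bear on the weight of the point and the choice of remedy; the gap remains.

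**Conclusion.** The concern holds in its conditional form. As written, the plan gives standard errors that are too small for the three count outcomes whenever patient rates vary beyond arm, site, depression level and one year of prior use.

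With 300 clinic patients, gamma rates of assumed shape 2 and mean 1 to 4, and an assumed two-sided 5% level, false-positive rates are about 9% to 13% with log(count + 1), and up to 15.5% with the raw count. Across the other shapes tried, the log form gives about 7% to 15%. If counts are more regular than Poisson, the test is conservative instead.

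Only the standard errors, intervals and p-values of these three outcomes are in question. The rate ratios, COMM, the primary pain-interference analysis and the sample size are untouched. It should be fixed, since the remedy is cheap and the outcomes support a named hypothesis.

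**What to change.** Add one sentence to the SAP under Analysis of Secondary Outcomes: all three counts will be analysed by Poisson regression with the planned covariates and offset, using robust (sandwich) standard errors, and the Pearson dispersion estimate will be reported beside each rate ratio. Protocol section 9.4.2 should be aligned with it.

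Model, data and software stay the same. Intervals widen if counts are over-dispersed: on the log scale by 13% to 27% in the shape 2 illustration with log(count + 1), and by up to 33% with the raw count, where part of the increase is misfit. They narrow if counts are under-dispersed. The sandwich test runs slightly above nominal at this sample size, at about 6% in the shape 2 setting and up to 7.5% in the most extreme gamma case tried (shape 1, raw count).

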## 9.4 STATISTICAL ANALYSES

### 9.4.1 GENERAL APPROACH

All primary and secondary analyses will be preceded by descriptive analyses of baseline and clinical characteristics. Summary statistics will include means and standard deviations for continuous variables, and sample proportions for categorical variables. Median and inter-quartile range values will accompany continuous variables that are non-normal. Results will be presented for the entire sample and stratified by intervention arm. We will assess between-arm imbalance of baseline covariates by calculating standardized mean differences. For continuous variables, we will assess normality by visually inspecting univariate distribution via a normal probability plot. Transformations will be implemented if required.

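### The three health care use models name no scale for the prior-year count and no allowance for overdispersion; log(1 + count) with corrected standard errors would be a safer choice

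*SAP*

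**What the plan says.** Under Analysis of Secondary Outcomes the SAP states: "Health care use will be compared between study arms using generalized linear models to account for count data (i.e., Poisson regression". The outcomes are "the number of opioid prescriptions, number of emergency department visits, and number of hospitalizations over 12 months after study entry". On the remaining terms it says "Predictors will include the study arm, study site, and baseline depression level" and "We will offset each model by the participant's time in the study". For prior use it says "The corresponding health care use in the 12 months before study entry will be entered as a covariate in each model". Protocol section 9.4.2 has the same sentence in nearly the same words: "The corresponding health care utilization in 12 months prior to study entry will be entered as a covariate in each model".

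The log link is not named, but Poisson regression with a time offset implies it. Neither document says whether prior use enters as the count, its logarithm or categories. Neither mentions overdispersion, a negative binomial model, or robust or scaled standard errors.

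Protocol section 9.4.1 has a general sentence, "Transformations will be implemented if required". It follows a normality check on continuous variables, does not mention prior-year counts, and is not carried into the SAP.

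These data exist only for clinic patients. The SAP, under Medical Outcomes, says: "For patients recruited at one of the six clinical sites, we will evaluate objectively measured opioid medication prescriptions and refills". Protocol Table 5 plans 300 of the 350 participants from clinics.

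**The concern.** With a log link, a raw-count covariate means that each additional prior visit multiplies expected follow-up visits by the same factor. If follow-up use is closer to proportional to prior use, that shape is wrong. A few very heavy users then get large leverage, the fit for everyone else suffers, and part of the precision that the covariate could give is lost.

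The choice of standard error interacts with this. Plain Poisson errors assume that variance equals mean once the covariates are in the model. If patients' underlying rates vary more than the covariates explain, the stated errors are too small whichever scale is used. Hypothesis H3 on health care use would then be tested at well above its nominal level.

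**Working it through.** **Is there a figure in the plan to reproduce?** Not for these models. The only power statement (350 participants, 80% power, 0.37 SD, 15% attrition) concerns continuous outcomes. At two-sided 0.05 with 350 × 0.85 / 2 = 148.75 evaluable per arm, the detectable difference is (1.960 + 0.842) × √(2/148.75) = 0.325 SD. The stated figure is therefore conservative, and it says nothing about the counts.

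**The two functional forms.** Let X be the prior 12-month count and t the time in study:

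- Raw: E(Y) = t × exp(α + β·arm + site + depression + γX), so prior use acts through exp(γX).
- Log: E(Y) = t × exp(α + β·arm + site + depression) × (1 + X)^γ, so prior use acts through a power. It is close to proportional when γ is near 1.

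**Inputs.** From the documents: N = 300 clinic patients (protocol Table 5), 1:1 allocation, the Poisson model with arm, site, depression level and a time offset. Assumed, because the documents give none: event means, spread of rates, year-to-year correlation and the arm effect.

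**First simulation set** (rate ratio 0.8, 15% with partial exposure, 2,000 trials per scenario). Correlation is between the observed counts in the two years. For gamma rates, CV-squared = 1/k.

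| Assumed use | Correlation | Variance ratio, log/raw | SE change |
|---|---|---|---|
| gamma, mean 0.5, k=1 | 0.34 | 0.96 | −1.9% |
| gamma, mean 1, k=1 | 0.50 | 0.91 | −4.6% |
| gamma, mean 1.5, k=1 | 0.60 | 0.82 | −9.4% |
| gamma, mean 3, k=5 | 0.41 | 0.99 | −0.5% |
| gamma, mean 3, k=2 | 0.60 | 0.86 | −7.2% |
| gamma, mean 3, k=1 | 0.74 | 0.66 | −18.6% |
| gamma, mean 3, k=0.5 | 0.84 | 0.39 | −37.6% |
| gamma, mean 10, k=4 | 0.70 | 0.86 | −7.1% |
| gamma, mean 10, k=1 | 0.88 | 0.32 | −43.7% |
| lognormal, mean 1 (two cases) | 0.10, 0.20 | 1.00 | about 0 |
| lognormal, mean 3 (four cases) | 0.18 to 0.40 | 0.89 to 1.00 | −0.1% to −5.5% |
| lognormal, mean 10 (two cases) | 0.47, 0.66 | 0.95, 0.74 | −2.7%, −14.2% |
| near-monthly prescriptions with a ceiling | 0.68 | 0.96 | −2.0% |

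**Second set** (lognormal rates, mean 1 to 8, CV-squared 0.5 to 2, correlation 0.4 to 0.8): variance ratio 0.70 to 1.01.

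**Third set** (rate ratio 0.75, mean 2 to 12, CV-squared 1 to 2, Pearson-scaled errors, correlation on the latent scale, 500 trials per cell):

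- Correlation 0.8: ratio 0.65 to 0.96, power +0.4 to +12 points.
- Correlation 0.6: ratio 0.81 to 0.96, power +1 to +5 points.
- Correlation 0.4: ratio 0.93 to 1.02, power −1 to +3 points, close to simulation noise.

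**What the planned standard errors would show.** Take gamma, mean 3, k=1. The true SD of the arm log rate ratio falls from 0.114 (raw) to 0.093 (log), and (0.093/0.114)² = 0.67, in line with the 0.66 in the table. The model-based Poisson SE is 0.072 on both scales, so the gain is invisible. It also understates the truth by a factor of 0.114/0.072 = 1.58 (raw) or 0.093/0.072 = 1.29 (log). The implied two-sided error is 2 × [1 − Φ(1.96/1.58)] ≈ 22% and 2 × [1 − Φ(1.96/1.29)] ≈ 13%. The simulated values were 22% and 12%.

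Across the first set, model-based type I error was 8% to 48% (raw) and 8% to 41% (log). In the second set it was about 10% to 66% whichever scale was used. With robust errors, the first set gave 4% to 11% (raw) and 4% to 7% (log). Robust-error power at mean 3, k=1 rose from 60% to 69%.

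**Negative binomial model** (400 trials per scenario), variance ratio log/raw:

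- Mean 1.5, k=1: 0.93.
- Mean 3: 0.99 (k=2), 0.87 (k=1), 0.63 (k=0.5).
- Mean 10, k=1: 0.58.

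The scale still matters under this model, but often less: 0.87 against 0.66 at mean 3, k=1.

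**The case against.** The strongest reply is that the plan never chose the raw count. It names no scale, and the protocol's general sentence shows that transformation is not ruled out. That is correct as far as it goes. A reader might infer that prior use is entered on the wrong scale, but the documents support only that the scale is unstated. The general sentence does not settle it, since it concerns continuous variables and is missing from the SAP.

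A reader might also infer that log(1 + count) would make this trial's comparison clearly more precise. The documents do not support that either. With no rates, dispersion or correlation, the trial cannot be placed in the table. The ceiling scenario for prescriptions, one of the three outcomes, gave only a 2% smaller SE. A guaranteed minimum gain cannot be claimed: the floor is about zero.

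A third reply is that overdispersion matters more than the covariate scale. That stands, and it is why the fix covers both. It is also fair to say that adjusting for prior use is already good practice and that functional form is partly preference.

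**Conclusion.** The point holds as a gap in specification with a nearly free improvement. It is not an error in a stated choice. Log(1 + prior 12-month count) was never materially worse than the raw count: the highest variance ratio was 1.02, within simulation noise. The gain runs from about 0% of the variance, where means are low, dispersion is mild or year-to-year correlation is about 0.4 or less, to 30% or more where use is strongly skewed and persistent. All of this rests on assumed inputs.

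The firmer part is the standard error. Plain Poisson errors were too small on either scale wherever rates varied between patients, with type I error of about 10% to 66% for CV-squared of 0.5 to 2. Changing the scale alone does not repair that. Only the secondary health care use outcomes are affected; the primary pain interference analysis is not.

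**What to change.** In the SAP (Analysis of Secondary Outcomes) and protocol section 9.4.2, state two things before any unblinded analysis:

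1. Prior use enters each of the three models as log(1 + prior 12-month count).
2. Inference uses a negative binomial model, or Poisson regression with robust or dispersion-corrected standard errors, in place of plain Poisson errors. Name one of these in advance.

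This needs two short wording changes and no new data. The cost is small. Confidence intervals for the health care use outcomes in H3 will be wider than plain Poisson would report, and the added 1 is a fixed, somewhat arbitrary way to handle patients with no prior use.
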